A Comparison of Pre-oxygenation Techniques in Pregnant Patients Prior to a
Cesarean Delivery - A Randomized Clinical Trial

NCT03310723

10/23/2019

Study Protocol and Statistical Analysis

Study was approved by the University of British Columbia Children's and Women's Research Ethics Board

Inclusion criteria: healthy, term (≥ 36 weeks gestation), non-labouring parturients admitted for elective caesarean delivery or induction of labour

Exclusion criteria: ASA physical status 3 or above; any medical condition that could affect gas exchange; BMI ≥ 40 kg/m²; known airway pathology; obstructed nasal airway; or unable to tolerate a tight-fitting facemask.

Microsoft Excel 2010 was used to generate a randomisation sequence with 1:1 allocation to either HFNO or control groups.

All patients were first placed in a 30-degree head up position using the Troop™ (Goal Medical, LLC, Eugene, OR, USA) elevation pillow and with a right lateral pelvic wedge to minimise aortocaval compression. A nose clip was applied and each patient was asked to breathe 21% oxygen at 12 l.min⁻¹ through a standardised mouthpiece using tidal volume breathing. The mouthpiece was connected to an anaesthetic circle system with a two-litre reservoir bag, heat moisture exchange filter and an oxygen analyser. At the end of 30 s, baseline values for oxygen saturation, respiratory rate, heart rate and EtO₂ were recorded.

Patients in the standard oxygen flow rate facemask group (control) were then pre-oxygenated with 100% oxygen, using tidal volume breathing and a tight-fitting facemask attached to a circle system, with an oxygen flow rate of 15 l.min⁻¹. End-tidal carbon dioxide waveform analysis was monitored to ensure a tight seal was achieved between the patient and the facemask. After 3 min, patients were asked to hold their breath for a few seconds and the nose clip was re-attached. The patients then exhaled fully and continued to breathe for several breaths via the mouthpiece (delivering 21% oxygen) to ensure the highest value for EtO₂ was measured.

Patients in the HFNO group were pre-oxygenated with 100% oxygen using tidal volume breathing and the Optiflow™ HFNO nasal high-flow cannula system (Fisher and Paykel Healthcare Ltd, Auckland, New Zealand). The oxygen flow rate was initially started at 30 l.min⁻¹ and gradually increased to a maximum of 70 l.min⁻¹ over the first 30 s. If a patient did not tolerate the flow rate, it was

Study Protocol and Statistical Analysis

reduced to a level the patient could tolerate, typically 50–60 L.min⁻¹. Patients were specifically instructed to breathe via their nose with a closed mouth and the percentage of time this was achieved was recorded (0%, 25%, 50% or 100%). After 3 min, the patients were asked to hold their breath for a few seconds while the HFNO was quickly removed and the nose clip re-attached. The patients then exhaled fully and continued to breathe for several breaths via the mouthpiece (delivering 21% oxygen) to ensure the highest value for EtO₂ was measured.

Patients in both groups then underwent a washout period for up to 5 min until the EtO₂ returned to within 10% of their baseline value. Once washout was completed, both groups repeated 30 s of tidal volume breathing followed by eight vital capacity breaths using their respective pre-oxygenation methods. During the initial 30 s of tidal volume breathing, the oxygen flow rate in the HFNO group was increased from 30 to 70 L.min⁻¹ and EtO₂ was measured at the conclusion of eight vital capacity breaths. The time taken to complete 30 s of tidal volume breathing and eight vital capacity breaths was also recorded.

Immediately after the study, patient satisfaction was assessed using a 5-category Likert scale for acceptability (acceptable, slightly acceptable, neutral, slightly unacceptable or unacceptable) and comfort (completely comfortable, slightly comfortable, neutral, slightly uncomfortable or completely uncomfortable).

Outcomes

The primary outcome was EtO₂ after pre-oxygenation, with factorial comparisons also being made between HFNO and standard flow rate facemask, and also between 3 min of tidal volume breathing and eight vital capacity breaths.

The Secondary outcomes were the proportion of patients achieving an EtO₂ ≥ 90%, percentage of time patients had their mouths closed during HFNO pre-oxygenation and tolerability (comfort and acceptability) of both pre-oxygenation techniques.

Sample Size Calculation

Study Protocol and Statistical Analysis

The study sample size was determined based on a prior study demonstrating that the mean (SD) EtO₂ achieved following 3 min of pre-oxygenation in healthy, non-pregnant subjects with HFNO and facemask was 85.6% (6.4%) and 88.5% (6.2%), respectively. We initially powered the study for a non-inferiority comparison. The criterion for non-inferiority with respect to EtO₂ concentration achieved after 3 min was considered to have been met if the upper limit of a two-sided 95%CI for the absolute difference of EtO₂ concentration between groups was less than 10%. Using a non-inferiority design, assuming a non-inferiority margin of 10 and a standard deviation of 6.3, and that the HFNO group would have a mean approximately 3% lower than the control group, 26 patients (13 per group) were required to achieve a power of 90% with a type-1 error of 0.05. To account for attrition and study dropouts due to equipment errors (i.e. lack of a tight seal for waveform analysis), the sample size was increased to 40 (20 per group).

After patient recruitment we realised that as a physiological and not clinical study, a standard superiority design was more appropriate. Using a superiority analysis with 20 patients per group there would have been approximately 31% power to detect a difference in means of 3% with a standard deviation of 6.3.

Consequently, data for primary outcomes were analysed using mixed-effects linear regression. Mixed-effects models take into account the repeated-measures aspect of the data and control for correlations among measurements from the same patient. To determine if there was a difference in how the treatment groups responded, we tested for an interaction term between group and time-point. If a significant interaction was found, we followed it up with pairwise tests of the estimated marginal means between the groups at each time-point (e.g. HFNO baseline vs. control baseline) using the Kenward–Roger method to estimate confidence intervals, and controlling for multiple comparisons using Tukey's method. The proportion of patients achieving an EtO₂ ≥ 90%, comfort and acceptability was compared using Fisher's exact test. A p value < 0.05 was considered statistically significant. Statistical analysis was performed using RStudio version 1.0.153 (Integrated Development for R. RStudio, Inc., USA; <http://www.rstudio.com>) and R version 3.4.1, release date June 30, 2017 (The R Foundation for Statistical Computing, Austria).

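### The comparison of 3 min tidal breathing with eight vital capacity breaths is completely confounded with period, yet it is listed under the primary outcome; the randomised device comparison is not

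*Combined protocol and SAP*

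**What the plan says.** All references are to the combined protocol and SAP.

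- **Randomisation** (procedures text, before the Outcomes heading): "Microsoft Excel 2010 was used to generate a randomisation sequence with 1:1 allocation to either HFNO or control groups". No randomisation of manoeuvre order is described.
- **First manoeuvre** (procedures text): facemask patients "were then pre-oxygenated with 100% oxygen, using tidal volume breathing and a tight-fitting facemask attached to a circle system", for 3 min. For the other arm, "Patients in the HFNO group were pre-oxygenated with 100% oxygen using tidal volume breathing", also for 3 min.
- **Washout** (procedures text): patients "underwent a washout period for up to 5 min until the EtO₂ returned to within 10% of their baseline value". The text does not say whether 10% is relative or in percentage points, what happens if the target is missed at 5 min, or whether EtO₂ at the end of washout was recorded.
- **Second manoeuvre** (procedures text): "Once washout was completed, both groups repeated 30 s of tidal volume breathing followed by eight vital capacity breaths using their respective pre-oxygenation methods". No patient is described as having the reverse order.
- **Outcomes**: the primary outcome is the EtO₂ reached, stated "with factorial comparisons also being made between HFNO and standard flow rate facemask, and also between 3 min of tidal volume breathing". The sentence then names the eight-breath manoeuvre as the other side of that second comparison.
- **Analysis** (under Sample Size Calculation): a mixed-effects linear model with a group by time-point interaction. If the interaction is significant, the groups are compared at each time-point. No period, order or carry-over term is named.

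**The concern.** Calling the comparisons factorial suggests two factors, device and breathing manoeuvre, whose effects can each be estimated. Only device has that status. Manoeuvre takes one value in the first period and the other in the second, for everyone. A difference between the two EtO₂ values could come from the manoeuvre, from practice or fatigue, or from oxygen left over from the first run. A lack of difference could equally be two of these cancelling. A primary-outcome statement that eight breaths are better than, worse than or as good as 3 min would be read as an effect of the manoeuvre, and this design cannot identify that effect.

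**Working it through.** **1. The plan's own figure.** For the superiority design finally adopted, the plan gives about 31% power (20 per group, difference 3, SD 6.3). The standard error is 6.3 × √(2/20) = 1.99 and the noncentrality is 3/1.99 = 1.51. A two-sided t-test at 0.05 then has 31.2% power, so the figure reproduces. It concerns the devices. The plan gives no target difference or power for the manoeuvre comparison.

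**2. What can be estimated.**

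| Device | Period 1 | Period 2 |
|---|---|---|
| Facemask | 3 min tidal | 30 s tidal + 8 vital capacity |
| HFNO | 3 min tidal | 30 s tidal + 8 vital capacity |

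Write the mean as μ + α·device + β·manoeuvre + π·period + γ·device×manoeuvre, with facemask, 3 min and period 1 coded 0.

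- Manoeuvre equals period in every row. The second-minus-first difference estimates β + π for facemask and β + π + γ for HFNO. No contrast isolates β.
- The five-column matrix for 20 patients per arm has rank 4. If half of each arm had started with each manoeuvre, the rank would be 5. This uses no assumed figure.
- HFNO minus facemask is α in period 1 and α + γ in period 2. Neither contains π, so order does not confound the device comparison. The period 1 contrast also precedes any carry-over. Carry-over could enter the period 2 contrast and the interaction only if it differed by device, in practice if washout were less complete in one arm.

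**3. Possible size of residual oxygen (illustration).** With mono-exponential wash-in, the amount added to the second EtO₂ is residual × (C − E)/(C − B). The following values are assumed and are not in the documents: baseline B 14 to 18%, ceiling C 92 to 95%, final EtO₂ E 75 to 90%.

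| Residual at start of second run | Smallest | Largest |
|---|---|---|
| 10% relative | 1.4 × 2/78 = 0.04 | 1.8 × 20/77 = 0.5 |
| 10 percentage points | 10 × 2/78 = 0.3 | 10 × 20/77 = 2.6 |

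**4. Would the 5-min cap bind (illustration)?** Assume a fall from about 88% to 16% with a time constant of 60 s. After 300 s the excess is 72 × exp(−5) = 0.5 points. A relative 10% target (1.6 points) is reached at 60 × ln(72/1.6) = 228 s. On these values the cap is not reached.

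**5. What an order effect alone could do (illustration).** Take 40 pairs, the plan's SD of 6.3, and an assumed within-patient correlation ρ. The SD of the paired difference is 6.3 × √(2(1 − ρ)). With no manoeuvre effect at all, the chance of p < 0.05 in a paired t-test would be:

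| Order effect | ρ = 0.3 | ρ = 0.5 | ρ = 0.7 |
|---|---|---|---|
| 1 point | 13% | 17% | 24% |
| 2 points | 38% | 50% | 72% |

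The documents give no size or direction for an order effect.

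**The case against.** The strongest reply is that the trial is about devices. A fixed order keeps the 3-min measurement, on which the sample size rests, ahead of any earlier oxygen exposure in every patient. The washout has an EtO₂ target that is the same in both arms. The analysis text sets out between-group contrasts and no explicit within-patient test of the manoeuvres. All of this stands, and it limits the point. It does not remove it, because the Outcomes section still names the manoeuvre comparison under the primary outcome.

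A reader might infer more than the documents support:

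- **That the trial's main comparison is confounded.** The title uses the word techniques, and the secondary outcomes use it for the two devices. The randomised device comparison is not confounded with order (step 2).
- **That carry-over is as large as the effect sought.** The 3-point difference in the sample-size text is the assumed device difference, so it is no benchmark for the manoeuvres. Simple decay of a 10-point residual gives 10 × exp(−1) = 3.7 points when run length and time constant are both 60 s. That takes 10% as percentage points and every patient at the limit. It also implies only 63% wash-in, a second EtO₂ near 16 + 0.63 × (93 − 16) = 65% with an assumed baseline of 16% and ceiling of 93%.
- **That the 5-min cap leaves much oxygen behind.** Step 4 suggests it would rarely bind, though its time constant is assumed.
- **That the eight-breath device contrast is biased.** This needs carry-over to differ by device, and nothing in the documents shows that it did.

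**Conclusion.** The point holds for the breathing-manoeuvre comparison. Its confounding with period is complete, follows from the described procedures alone, and cannot be undone by any model term. The contrast is also not purely eight vital capacity breaths, since the second run includes 30 s of tidal breathing.

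Carry-over is a separate and lesser matter. Its size is unknown, and it is probably small if the 10% target is relative and was met. By itself it would raise the second value. Practice or fatigue could act in either direction.

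The randomised device comparison at 3 min is unaffected. The device contrast after eight breaths and the group by time-point interaction would be affected by carry-over only if washout completeness differed by device.

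**What to change.** 1. Remove the manoeuvre comparison from the primary outcome and drop the word factorial for it. Keep the randomised device comparison at 3 min as primary.
2. Report the manoeuvre comparison as descriptive and order-confounded, with no claim that either manoeuvre is better or that they are equivalent.
3. If the data were kept, report EtO₂ at the end of washout by device and the number of patients who reached the 5-min cap. Add a sensitivity analysis that adjusts the second measurement for end-of-washout EtO₂. This addresses residual oxygen, not order. If the values were not recorded, say so.
4. State whether the 10% washout tolerance was applied as relative or as percentage points.

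The cost is wording and, where data allow, one sensitivity analysis. The trial gives up a confirmatory statement on the manoeuvre, which the design could not support.

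Randomising manoeuvre order within each device group, with a period term in the model, applies only to a repeat study, because the text says that recruitment was already over. It has a price there too: half of the 3-min measurements would follow an earlier manoeuvre, and a period term would not remove device-specific carry-over.

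### Under the plan's own 95% confidence-interval rule, 13 per group give about 78–81% non-inferiority power, not the stated 90%, which would need 18–19 per group

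*Combined protocol and SAP*

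**What the plan says.** All of this is in the Sample Size Calculation section. The non-inferiority rule is that the "upper limit of a two-sided 95%CI for the absolute difference of EtO₂ concentration between groups was less than 10" percent, applied to end-tidal oxygen after 3 minutes. The calculation is then described as "assuming a non-inferiority margin of 10 and a standard deviation of 6.3", and as expecting that "the HFNO group would have a mean approximately 3% lower than the control group". From these inputs the plan concludes that "26 patients (13 per group) were required to achieve a power of 90% with a type-1 error of 0.05". It does not say whether the 0.05 is one-sided or two-sided.

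The target was then raised to 20 per group to cover dropout and equipment problems. No dropout rate is given. The section goes on to say that, after recruitment, superiority was judged the better design. It puts the power of 20 per group for a 3-point difference at roughly 31%.

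**The concern.** The decision rule and the power statement stand next to each other and should describe the same test. Requiring the upper bound of a two-sided 95% interval to lie below the margin is a one-sided test at 2.5%. Every input needed to compute its power is printed in the paragraph, and those inputs do not give 90% at 13 per group.

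What is at stake is the justification for the sample size. This paragraph is the only stated reason for enrolling 40. A reader who accepts 13 evaluable patients per group as enough would think that losses for poor mask seal could be absorbed comfortably. At 13 per group the chance of missing non-inferiority, if the assumptions hold, is about 19–22%, roughly double the 10% that the plan states.

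**Working it through.** **Inputs, all from the Sample Size Calculation section except the allocation ratio**

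- Margin: 10 percentage points.
- Standard deviation: 6.3. The prior-study values of 6.4 and 6.2 pool to √((6.4² + 6.2²)/2) = 6.30.
- Expected deficit: 3. The prior-study means give 88.5 − 85.6 = 2.9.
- Distance from the expected difference to the margin: 10 − 3 = 7. The difference is taken as control minus high-flow nasal oxygen.
- Allocation: 1:1 (randomisation statement at the start of the document).
- One-sided alpha: 0.025, from the 95% interval rule.

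**Can the plan's figure be reproduced?**

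The normal-approximation formula is n per group = 2 (z_α + z_β)² (SD / distance)², with (6.3/7)² = 0.81.

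- One-sided 0.05, 90% power: 2 × (1.645 + 1.2816)² × 0.81 = 13.87, so 14. This is close to 13 but does not equal it.
- One-sided 0.025, 80% power: 2 × (1.960 + 0.842)² × 0.81 = 12.72, so 13. This matches, but at a different power.
- One-sided 0.025, 90% power, which is the plan's rule and its stated power: 2 × (1.960 + 1.2816)² × 0.81 = 17.02, so 18.

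The stated 13 is therefore not reproduced under the plan's own rule and stated power.

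**Power at fixed n under the stated rule (one-sided 0.025, distance 7)**

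The noncentrality is 7 / (6.3 √(2/n)). At n = 13 this is 7 / 2.471 = 2.833. The normal approximation gives Φ(2.833 − 1.960) = Φ(0.873) = 80.9%. The t version uses the noncentral t distribution with 2n − 2 degrees of freedom.

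| n per group | Normal | Noncentral t |
|---|---|---|
| 13 | 80.9% | 77.6% |
| 17 | 89.96% | 88.1% |
| 18 | 91.5% | 89.9% |
| 19 | 92.9% | 91.5% |
| 20 | 94.0% | 92.8% |

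So 90% power needs 18 per group (normal) or 19 (t, since 18 falls just short). From 20 per group, that leaves 20 − 18 = 2 or 20 − 19 = 1 per group for losses, against 20 − 13 = 7 if the stated figure were right.

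**Sensitivity**

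- One-sided 0.05 with a deficit of 3: power at 13 is 88.3% (normal) or 86.6% (t), still below 90%.
- Most favourable reading (one-sided 0.05, deficit 2.9, normal): n = 13.49, so 14, and power at 13 is 89.0%. This contradicts the 95% interval rule and still falls short.
- Stated rule with a deficit of 2.9: power at 13 is 82.0% (normal) or 78.7% (t). The requirement is 17 (normal) or 18 (t), leaving 2–3 per group for losses.

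**Check on the method**

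For the plan's superiority figure (20 per group, difference 3, standard deviation 6.3, two-sided 0.05), the same approach gives 31.2% by t and 32.5% by normal. The stated figure of about 31% is therefore reproduced, and the inputs are being read correctly.

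**The case against.** The strongest reply is that nothing now depends on this figure. The plan says that superiority replaced non-inferiority after recruitment, the analysis described is a mixed-effects model with a group-by-time interaction, and no conclusion is drawn against the 10-point margin. The target of 20 per group exceeds what the 95% rule needs. All of this stands, and it limits the importance of the point. It does not make the power statement correct.

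A second reply is that the 0.05 may have been meant as one-sided. The text leaves that open, but the stated rule does not, and even one-sided 0.05 gives only 86.6–88.3% at 13 per group.

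Three stronger readings are tempting, and the documents do not support them.

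- A reader might infer that the plan promises 90% power after losing 14 of 40 patients. It gives no tolerated number of losses and no dropout rate. The 7 per group is only the difference between two stated sample sizes.
- A reader might infer that the authors must have used a one-sided 5% test. The number 13 fits 80% power at one-sided 2.5% exactly after rounding, and fits 90% at one-sided 5% only nearly. The documents do not show which slip occurred.
- A reader might infer that the planned trial was too small for its non-inferiority aim. At 20 per group it was not, if losses were few. The documents do not report losses, so no actual harm can be shown.

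**Conclusion.** The stated power is wrong as written. Under the plan's rule and inputs, 13 per group give 77.6% (t) or 80.9% (normal) instead of 90%, and 90% needs 18 (normal) or 19 (t) per group. The 20 per group planned give 92.8% (t) or 94.0% (normal) with no losses, so the room for losses at 90% power is about 1–2 per group.

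This rests on a two-group comparison of means at 3 minutes, equal allocation, a common standard deviation of 6.3 and a true deficit of 3. Using 2.9 moves the requirement down by one per group and does not change the conclusion.

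Importance is low to moderate. It is a correction to the sample-size justification and does not invalidate the enrolment target or the superiority analysis.

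**What to change.** Keep the existing sentence, since it records what was calculated at the time, and add a correction after it. Replacing it with a new sample size would present a calculation that is not shown to have been made before enrolment. Suggested wording:

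*Correction: the non-inferiority rule corresponds to a one-sided 2.5% test. With margin 10, SD 6.3 and a deficit of 3, 13 per group give 77.6% power (noncentral t) or 80.9% (normal approximation). For 90% power, 19 (t) or 18 (normal) per group are needed. The planned 20 per group give 92.8% (t) or 94.0% (normal) with no losses, so about 1–2 losses per group can be absorbed at 90% power.*

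If the sponsor's records show how 13 was obtained, say so. Do not switch the criterion to a 90% interval to fit the number, because that would loosen the decision rule after recruitment. No extra patients are needed.

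The cost is one added paragraph. The downside is that the stated power and the apparent room for attrition become less favourable.

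### The non-inferiority question at 3 min that the trial was sized for was replaced by superiority after recruitment, and the stated analysis may leave it unanswered

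*Combined protocol and SAP*

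**What the plan says.** All of this stands in the combined protocol and SAP under Sample Size Calculation, whose last paragraph also holds the analysis plan.

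- **Original design.** "We initially powered the study for a non-inferiority comparison". The criterion, for EtO₂ after 3 min, was that the "upper limit of a two-sided 95%CI for the absolute difference of EtO₂ concentration between groups was less than 10" per cent.
- **Sizing.** The calculation ran "assuming a non-inferiority margin of 10 and a standard deviation of 6.3", and expected that the "HFNO group would have a mean approximately 3% lower than the control group". On that basis "26 patients (13 per group) were required to achieve a power of 90% with a type-1 error of 0.05", and to allow for losses "the sample size was increased to 40 (20 per group").
- **The change.** "After patient recruitment we realised that as a physiological and not clinical study, a standard superiority design was more appropriate".
- **Power after the change.** "with 20 patients per group there would have been approximately 31% power to detect a difference in means of 3" per cent, with the same SD.
- **Analysis now stated.** A mixed-effects linear regression with a test of the group-by-time-point interaction. Only if that interaction is significant do comparisons of the groups at each time-point follow, with Kenward–Roger intervals and Tukey adjustment. The margin of 10 does not appear in this paragraph.

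The criterion does not state the direction of subtraction. With an upper limit as the test and HFNO expected to be lower, control minus HFNO is the only reading that fits, and it is used below.

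**The concern.** Two things happened together. The hypothesis was changed after patients had been recruited, and the analysis tied to the first hypothesis dropped out.

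The first matters because EtO₂ is measured within the study session. By the end of recruitment, the outcome data had been collected or nearly so. A hypothesis adopted at that stage does not have the standing of one fixed beforehand.

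The second matters more in practice. The between-group interval at 3 min is what the original criterion needs, and it now depends on a significant interaction. If the interaction is not significant, the plan yields no between-group interval at 3 min and makes no comparison with the margin. The reader is left with a non-significant test from a design that, by the plan's own figure, had low power for the difference it expected. Such a result cannot separate no difference from a modest deficit, yet it is easily read as showing that the techniques are alike.

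**Working it through.** **Inputs** (Sample Size Calculation): SD 6.3; expected deficit of HFNO 3 points; margin 10; 20 per group, or 13 per group as the number before the allowance for losses; two-sided 95% CI, equivalent to one-sided alpha 0.025 for non-inferiority; two-sided alpha 0.05 for superiority. Power is from the non-central t distribution.

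**Step 1. Reproduce the plan's 31%.**
- Standard error of the difference = 6.3 × √(2/20) = 1.992.
- Non-centrality = 3 / 1.992 = 1.51, with 38 degrees of freedom.
- Two-sided power = 31.2%. The stated figure reproduces.
- The chance of a non-significant two-group test at a deficit of 3 is 100 − 31.2 = about 69%.

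**Step 2. Power of the original criterion with the same inputs.**
- Distance to the margin = 10 − 3 = 7.
- Non-centrality = 7 / 1.992 = 3.51.
- Power = 92.8% (94.0% by the normal approximation). The plan does not state this figure; it follows from the plan's inputs.

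**Step 3. Expected interval.**
- Half-width = 2.024 × 1.992 = 4.03.
- Expected 95% CI = 3 ± 4.03, about -1.0 to 7.0. It includes 0 and lies below 10.
- In 100,000 simulated trials at a deficit of 3, 69% were non-significant for superiority. Of those, 99.9% had an upper limit below 10.

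**Step 4. The same losses applied to both tests.** With 13 evaluable per group, the standard error is 6.3 × √(2/13) = 2.471.
- Superiority: 3 / 2.471 = 1.21, power 21%.
- Non-inferiority: 7 / 2.471 = 2.83, power 78%. The plan's 90% at 13 per group is closer to a one-sided alpha of 0.05 (87% by t, 88% by normal) than to its two-sided 95% CI.

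**Step 5. Dependence on the assumed deficit** (20 per group, SD 6.3). The two distances are the deficit and 10 minus the deficit, so the powers mirror each other around 5.

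| True deficit | Non-inferiority power | Superiority power |
|---|---|---|
| 3 | 93% | 31% |
| 5 | 69% | 69% |
| 6 | 50% | 84% |
| 7 | 31% | 93% |

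Superiority power reaches 80% at a deficit of about 5.7 points. At a deficit of 3, 80% power would need about 71 per group.

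**Step 6. Should the test against 0 wait for non-inferiority?** The plan expects HFNO to be lower, so an interval that excludes 0 would most likely show HFNO to be worse. In simulation with 20 per group and a deficit of 8, the two-sided test is significant in 97% of trials. In about 84% of trials it is significant but non-inferiority fails, so a fixed sequence starting with non-inferiority would block the conclusion. At a deficit of 6 this happens in about 50%. The statement about 0 should therefore not be conditional on non-inferiority.

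**The case against.** The authors disclose the change, its timing, their reason and the low power. Nothing is concealed, and for a physiological comparison an estimate of the difference is a reasonable aim. The document does not say that anyone had looked at the outcome data when the change was made. All of this stands. It limits the point to the status of the new analysis and the loss of the planned one; it does not put the planned comparison back.

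A reader might infer that the likeliest result of the trial is a non-significant test. The documents do not support that without conditions. The 69% holds for a true deficit of 3, a value taken from healthy non-pregnant subjects, whereas this trial enrols term parturients. At a deficit of 7 the two powers are reversed. Moreover, the 31% belongs to a simple two-group comparison. The analysis stated is an interaction test in which baseline is one of the time-points, and no power is given for it.

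A reader might also infer that the data are uninterpretable, or that the trial swapped a question it could answer for one it could not. Neither follows. The expected interval of about -1.0 to 7.0 is informative, and the model can supply an interval at 3 min. The defect is the condition placed on reporting it. Nor do the documents claim equivalence; that is a risk in how a null result would be read.

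**Conclusion.** The point holds in limited form. A pre-specified non-inferiority comparison was replaced after recruitment. The analysis now stated omits its margin and makes the interval it needs conditional on a significant interaction, so the question that set the sample size can go unanswered.

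At a true deficit of 3 and an SD of 6.3, non-inferiority power is about 93% and superiority power 31% with 20 evaluable per group, or 78% and 21% with 13. These figures rest on independent-group comparisons at 3 min and on the assumed deficit, and they do not describe the power of the interaction test. The superiority and interaction analyses should be read as adopted after recruitment. The documents do not show whether the choice was influenced by the results.

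**What to change.** 1. Report control minus HFNO EtO₂ at 3 min with its unadjusted two-sided 95% CI, whatever the interaction p value.
2. Compare the upper limit with the pre-specified margin of 10, and present this as the originally planned analysis.
3. From the same interval, state whether 0 is excluded in either direction. Do not make this conditional on meeting non-inferiority.
4. Label the superiority and interaction analyses as adopted after recruitment (post hoc), and say whether outcome data had been seen when the change was made.
5. State that a non-significant result is inconclusive and is not evidence of no difference.

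The cost is one confidence interval from existing data and some wording in the SAP and report; no further patients are needed. The downside is that the trial must report against its original 10-point margin, which some readers may find wide. The interval lets them apply a narrower one.
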